## PROTECTION OF HUMAN PARTICIPANT(S)

This project meets the definition of a clinical trial. This section describes the Protection of Human Participants.

## HUMAN PARTICIPANTS INVOLVEMENT AND CHARACTERISTICS

All study procedures will be approved by the University of Michigan Medical School's Institutional Review Board prior to implementation. The proposed study will involve recruiting persons age 18 and above living in Hillsdale, Lenawee, Jackson, Calhoun or Branch County, Michigan, and screening interested persons located in the target communities. Informed consent will be procured following the screening. All subjects will be told that participation is voluntary and can be withdrawn at any time. Participants will also be advised that information provided will be kept confidential. Limits to confidentiality (i.e. prominent suicidal or homicidal ideation with imminent risk, child abuse) will also be discussed and provided in written format. Included persons will be aged 18 and older, residents of the target community for at least 12 months, with at least mild depressive symptoms (PHQ-9  $\geq 5$ ), who are not currently receiving psychosocial treatment. Persons will not be eligible for the study if they are (1) non-English speaking; (2) currently receiving regular psychotherapy for depression; (3) have ever completed a prior full course of CBT ( $\geq 8$  sessions); (4) meet criteria for any psychotic disorder; (5) current use of opiates or freebase cocaine; (6) have cognitive impairment ( $\geq 2$  incorrect items on the 6-item mini mental status exam); or (7) present with prominent suicidal/homicidal ideation with imminent risk. Persons will be screened for the presence of elevated depressive symptoms that are currently untreated, including suicide risk. Any participant determined to be at imminent risk for suicide will be referred to the psychiatric emergency services at the Dempster W. Muffitt Center for Psychiatric Care at the Hillsdale Community Health Center. If they refuse a referral, standard clinical safety protocol will be followed (see below).

**Gender and Minority Inclusion.** Participants will be recruited from Hillsdale, Lenawee, Jackson, Calhoun, or Branch County, Michigan through advertisements and referrals from local clergy and mental health, primary care, and human service providers. Given epidemiologic data on depression prevalence, it is expected that our sample will be 67% women and 33% men. Census data for Hillsdale county suggests the community is 97% white; 2% Hispanic, and 1% African American. Special attention will be made to recruiting minorities through

targeting churches with sizable Hispanic and African American congregations. Therefore, we expect to recruit approximately 90% White participants; 5% Hispanic participants; and 5% African American participants.

**Removing Participants from the Protocol.** Based on our experience, removal of participants from the protocol for clinical reasons is expected to be very rare, and established procedures are available to appropriately respond to various forms of clinical deterioration. Participants may be removed from the trial for the reasons listed below. In each case, participants will be consulted regarding potential removal. Final judgment for participant withdrawal will be made via consensus of group leaders, PI: [name], and Co-I: [name]. Effort will be made to continue assessment of any participants removed from the trial. Withdrawn participants will be referred for the best available treatment outside the research protocol.

*Clinical Deterioration.* During the active intervention phase, participants who experience clinical deterioration over time in treatment will be evaluated and removed from the trial. Clinical deterioration is defined as significant worsening of depressive symptoms, based on a 5 point increase on the PHQ-9 for those with scores of 10 and above. These participants will be contacted by a study team member and referred to local resources that can provide an increased level of care. Worsening suicidality or comorbid conditions that are determined to compromise participant safety will also be grounds for participant removal. These concerns may come to our attention directly via the group leaders, participants, or family members. Additionally, participants who endorse any level of suicidal ideation on the PHQ-9 ( $>0$  on question 9) will complete the Columbia Suicide Severity Rating Scale (C-SSRS). Participants whose scores indicate low risk for suicidal ideation on the C-SSRS will continue participating in the intervention and their suicidal ideation will be monitored weekly during that time. Participants whose scores indicate moderate or high risk for suicidal ideation on the C-SSRS will be connected to clinical back-up, connected to appropriate resources, and monitored. A safety-monitoring plan will be in place for participants experiencing worsening severity during the waiting period prior to treatment assignment or during the follow-up period.

In addition, at first contact, participants will be provided with an information sheet detailing procedures for contacting investigators should their depressive symptoms, comorbid symptoms, or risk for harm to self or others become a source of concern. If any of the scheduled reassessments reveal worsening depressive symptoms, comorbid symptoms, or risk for harm to self or others, a repeat face-to-face assessment will be completed, including the PHQ-9, CSRSS, BDI, and MINI. If there is a clinically significant worsening on the PHQ-9 or CSRSS relative to the prior assessment, significant effort will be made to expedite entry into the best available treatment outside the research protocol.

*Treatment Non-Participation.* If a participant does not participate in a session they will be counseled by one of the group leaders and a plan will be put in place to encourage participation. If a participant misses three consecutive sessions and the group leader cannot reach them, the group leader will stop reaching out. Study team members will still reach out to invite the participant to complete follow up assessments and document their reasons for discontinuing treatment.

*Interference with group process.* If a participant interferes with the group process due to extremely disruptive behavior, the participant will be counseled to minimize interference. If the disruptive behavior persists, they will be removed from ROST treatment.

## SOURCES OF MATERIAL

Data will be collected only with written informed consent from the participant. Two sources of data will exist for this study. First, participants will respond to structured assessments created to gather screening, baseline, and follow-up data. The majority of proposed instruments have been widely used. Second, digital recordings of semi-structured qualitative interviews focused on intervention group participants' perceptions of the intervention, audio recordings of the focus groups conducted after each open pilot session, and audio recordings of all open pilot and RCT sessions will be collected to ensure treatment integrity. Such recordings will only be gathered with informed consent. All of the information will be collected specifically for this research project. Participant identifying information (i.e. name, address, telephone number) will be kept separate from

their responses. Identification codes will be assigned to participants. These codes will also be kept separate from identifying information except for the purpose of follow-up interviews. These connections will be destroyed once the data is collected.

Data, coded only with unique identifying code numbers, will be stored separately of identifying information. All data will be stored in locked files, accessible only to the Principal Investigator and key study personnel. All data collected via paper measures will be scanned and stored on password protected computers on the University of Michigan's secure server. REDCap will be used to electronically collect data at each session during active groups. University of Michigan has a license with REDCap and the program is HIPAA compliant. Data collected electronically will be exported from REDCap and stored on password protected computers on the University of Michigan's secure server. All published reports will contain data reported either in aggregate form (where no individual responses can be identified) or in composite individual examples that are constructed so that identification is not possible. In addition, all levels of staff will have completed the University of Michigan's web-based Program for Education and Evaluation in Responsible Research and Scholarship (PEERRS).

## POTENTIAL RISKS

Participants are revealing personal information about themselves in this study, through structured assessments and through audio recorded qualitative interviews, focus groups, and intervention group sessions. Thus, the primary risk to participants in this study is confidentiality of the data, should it be inadvertently released. Rigorous confidentiality procedures have been developed to minimize the risk of breaches and participants will be informed of procedures to protect their confidentiality. Therefore, there is minimal risk that confidentiality will be violated. The limits of confidentiality will be explicitly described to participants by research personnel.

Although the study does not specifically inquire about risk of harm to others or child abuse, these details may emerge during the course of interviews or the intervention. Mandatory reporting laws will be explained prior to all participants as part of the consent process.

There is also a slight risk of psychological discomfort to participants from the questions asked as part of research assessments and interviews. All research personnel will be trained to respond to emotional distress resulting from the study protocol and to refer to appropriate community resources as necessary.

The ROST intervention will be delivered by group leaders (clergy) with strong interpersonal skills who will receive training and supervision from the Principal Investigator and co-Investigators (Drs. [name], [name], [name]). The group leaders will have access to clinical backup from Drs. [name] and [name]. In previous trials of CBT there have been few reported cases of uncontrollable distress; however, it is always possible that negative reactions may arise. In these circumstances, group leaders will follow our risk management protocol which involves contacting either [name] or [name], following through with strategies that are empathic and non-blaming, and encouraging immediate engagement with supportive close others and with ongoing professional mental health assistance.

## Protection Against Risks.

*Recruitment and Informed Consent.* Informed consent will be procured in-person, prior to the initial baseline interview. All participants will be told that participation is voluntary and can be withdrawn at any time. Participants will also be advised that information provided will be kept confidential. Limits to confidentiality will be discussed and provided in written format (i.e. prominent suicidal or homicidal ideation with imminent risk, child abuse).

*Protection Against Risk.* We do not consider the time demands on participants a serious risk for two reasons. First, the informed consent procedures emphasize the fact that the interviews are voluntary and can be terminated at any time. Second, the participants will be paid a nominal fee of \$25 for assessments at baseline, post-treatment, and 3-month follow-up; and \$20 for completion of a qualitative interview at follow-up. Participants completing ROST will receive \$10 for each session they attend. These payments compensate for

the time demands made on respondents by their participation and travel expenses. In addition, study personnel will be trained to minimize these time burdens in whatever way they can, particularly by scheduling assessment interviews at times that are convenient to respondents and encouraging them to take breaks or tend to their personal needs as they wish.

The potential risks of breached confidentiality are more serious, and we have taken a number of special precautions. First, research personnel will complete training sessions on all stages of confidentiality, including personal contact, telephone contact, and data records and management. The importance of maintaining confidentiality will be emphasized at all times. Breaches in confidentiality by staff members will be grounds for dismissal.

Participants' identifying information (i.e. name, address, phone number, email address) will be kept separate from their responses. Identification codes will be assigned to participants. These codes will also be kept separate from identifying information except for the purpose of follow-up interviews. These connections will be destroyed once the data is collected.

Concerns about confidentiality continue after the interviews are completed. Data, coded only with unique identifying code numbers, will be stored separately from identifying information. All data will be stored in locked files, accessible only to the Principal Investigator and key study personnel. All data collected via paper measures will be scanned and stored on password protected computers on the University of Michigan's secure server. REDCap will be used to electronically collect data at each session during active groups. University of Michigan has a license with REDCap and the program is HIPAA compliant. Data collected electronically will be exported from REDCap and stored on password protected computers on the University of Michigan's secure server. All published reports will contain data reported either in aggregate form (where no individual responses can be identified) or in composite individual examples that are constructed so that identification is not possible. In addition, all levels of staff will have completed the University of Michigan's web-based Program for Education and Evaluation in Responsible Research and Scholarship (PEERRS). The principal investigator and mentors have already completed certification of this training.

Based upon the mentorship team members' experience with similar studies, there is minimal risk of subjects becoming emotionally distressed by the assessment interview process or participation in the intervention. Participants are instructed that they can terminate the assessment interview at any point or refuse to answer any questions. Further, assessment interviewers will be instructed to terminate an interview whenever they feel that it is creating genuine distress for a participant. Group leaders will be trained in how to appropriately and sensitively handle distress, should it emerge during the intervention. (see distress protocol above).

#### *Protections for Participants with Suicide Risk*

The primary risk with the proposed study is suicide risk. This research will follow a comprehensive protocol for responding to suicide risk based on the University of Michigan Health System (UMHS) suicide risk assessment standards. In every case, if a participant is determined to be at risk for suicide, several steps will be followed: (1) ongoing contact with the participant will occur until risk is determined to be minimal; (2) the investigators will be informed immediately and continuously apprised of any changes/developments in the participant's risk for suicide; (3) all assessments, conversations, and steps taken with the participant to ensure safety will be thoroughly documented; (4) we will communicate with our IRB to determine the need for adverse event reporting, and any actions taken or outcomes will be reported to the IRB and NIH. All participants will be initially interviewed in-person by trained research associates who have clinical experience and graduate level mental health training. This methodology allows for intervention should suicide be a risk. Interviewing clinicians will be trained in risk assessment and will receive ongoing training throughout the course of the study. All participants will be assessed for suicide risk using the UMHS suicide risk assessment protocol. If a participant is determined to be at risk based on clinical assessment, the research associate will contact [name] or [name] by phone or text. If risk is determined during the intervention based upon results of measures completed electronically during sessions or via participant disclosure of suicidal ideation, group leaders will contact [name] or [name] by phone or text. In both cases, [name] or [name] will then contact the

participant immediately and further assess suicide risk. If risk is determined to be present, the standard clinical protocol for responding to suicide risk will be implemented.

The protocol is as follows:

(1) Mild Risk (e.g., suicidal ideation present without presence of current plan, low intent, presence of hope, no current means)

- a. The individual will be encouraged to call the local Psychiatric Emergency Service.
- b. The individual will be encouraged to discuss feelings with family members. Should family members be present at the time of the interview, their immediate involvement will be enlisted.
- c. Follow-up contact will be provided by the research team until risk is determined to be minimal.

(2) Moderate Risk (e.g., suicidal ideation present with additional risk factors: moderate intent, low hope, possible plan and/or possible means)

- a. The individual will be encouraged to call the local Psychiatric Emergency Service.
- b. If the individual refuses to call PES, we will enlist the assistance of a family member in doing so.
- c. If the individual refuses to enlist family, or if family is not present, the individual will be encouraged to have the clinician call. Should the individual refuse, and if no one is in the home to ensure ongoing safety, the clinician will make the phone call against the individual's will.
- d. A plan for removing from the home any means with which to commit suicide, preferably with the assistance of family or trusted others.
- e. Continuous follow-up phone contact ensuring the participant's safety throughout the day and then on a daily basis until risk is determined to be mild. Phone calls will then occur less frequently until risk is determined to be minimal. The participant will be told at the outset of participation that, if suicide risk is present and they cannot be reached by phone, that the local safety authority or police will be called.

(3) High Risk (e.g., suicidal ideation present with several additional risk factors: high intent, no hope, a definite plan, and current means)

- a. The individual will be encouraged to call the local Psychiatric Emergency Service.
- b. If the individual refuses to call PES, we will enlist the assistance of a family member in doing so.
- c. If the individual refuses to enlist family, or if family is not present, the individual will be encouraged to have the clinician call. Should the individual refuse, and if no one is in the home to ensure ongoing safety, the clinician will make the phone call against the individual's will. PES will send a unit or the police to the home.
- d. The clinician will remain present in the home or in constant telephone contact until the participant's safety is ensured. Should the participant refuse hospitalization and it is deemed necessary, the clinician will engage police and authorities in ensuring involuntary hospitalization.
- e. Any potential means with which to commit suicide will be removed from the home, preferably with the assistance of family or trusted others.
- f. On-going follow-up will occur until it is determined that risk is minimal.

The comprehensive written informed consent document will outline potential limits of confidentiality based on suicide risk and on suspicion of child abuse and neglect. Participants will be notified of the clinical researcher's obligation to act in a manner that is most protective of their own safety and the safety of their children. In situations of suspected abuse and neglect, we will use procedures identical to those in place at the UMHS Department of Psychiatry.

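### High-risk suicide steps send responders to the home, but no step confirms where a participant on a phone or Zoom contact is

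*Combined protocol and SAP*

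**What the plan says.** All references are to the combined protocol and SAP.

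**The risk steps** (Protections for Participants with Suicide Risk). In moderate-risk item c and high-risk item c, a clinician may call the emergency service against the person's will, after refusals, "if no one is in the home to ensure ongoing safety". High-risk item c then states: "PES will send a unit or the police to the home". High-risk item d reads "The clinician will remain present in the home or in constant telephone contact", and if hospitalization is needed but refused, "the clinician will engage police and authorities in ensuring involuntary hospitalization". Moderate-risk item e relies on telephone follow-up and warns participants at the outset about what happens "if suicide risk is present and they cannot be reached by phone, that the local safety authority or police will be called".

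**The premise.** The same section says "All participants will be initially interviewed in-person by trained research associates", and adds: "This methodology allows for intervention should suicide be a risk".

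**Modes of contact.** Baseline Interview and Follow-up interviews each allow in-person, phone or videoconference contact. Study Sites and In-Session Measures allow virtual ROST sessions. Assessment retention also offers interviews at the participant's home.

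**Location data.** Maintenance of samples has addresses, phone numbers and emails collected within the baseline assessment and updated regularly. It also asks for contact persons living elsewhere who would know where the participant is. The earlier contact form (Recruitment) asks for phone, contact persons and email, but no address.

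**The concern.** The protocol names suicide risk as the primary risk of the study. When a participant is on a phone or Zoom call, staff cannot see where that person is. If high-risk item c is followed as written, help goes to the residence even if the person is at work, in a parked car or at a relative's house. A clinician can ask once risk appears, but by then the participant may refuse to say or may disconnect. Protection Against Risks tells participants that they may end an assessment interview at any point.

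Location also decides whom to call. Participants come from five counties, while the psychiatric emergency service named under Human Participants Involvement and Characteristics is in Hillsdale. Both arms are affected: control participants have remote options at baseline, post-treatment and follow-up. What is at stake is a rare but possibly irreversible failure of a safety procedure. The trial's inference is not at stake.

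**Working it through.** The documents give no figure to reproduce here, so the check sets the sections side by side.

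**1. How the risk steps use the home.** The home is mentioned six times:

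| Item | Use | Depends on current location? |
|---|---|---|
| Moderate c | whether anyone is there to keep the person safe | yes, for a remote contact |
| Moderate d | removing means | no |
| High c | whether anyone is there to keep the person safe | yes, for a remote contact |
| High c | where responders are sent | yes |
| High d | clinician present, or on the telephone | no, a telephone route is given |
| High e | removing means | no |

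Three of the six (1 + 2) depend on where a remote participant is, and three are sound as they stand. Only high-risk item d puts the clinician in the home.

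**2. What staff would know.** The address on file is a residence, held for retention and not linked to the risk steps. The contact persons might help, but they do not live with the participant, and the risk steps do not mention them. No supplied section asks for current location, either when contact begins or when risk is found.

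**3. Following a remote high-risk case.** The participant declines to call; family cannot be enlisted or is absent; the participant declines to let the clinician call; no one is in the home; the clinician calls anyway; responders go to the home. The outcome is right if the participant is at home and wrong if not. The telephone route in item d keeps the line open but does not tell responders where to go. The police call in moderate-risk item e has the same limit.

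**4. The in-person premise.** Protections for Participants with Suicide Risk has everyone first interviewed in person; Baseline Interview allows phone or Zoom. Protection Against Risks has consent obtained in person; Consent allows Zoom with an electronic signature. Both statements conflict with the procedures.

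**5. Size.** The number of misdirected responses would be contacts × share remote × rate of reaching high-risk item c × share away from home. The documents give none of the last three, so no event count is possible.

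The workload of a location question can be bounded if every contact were remote, using the planning numbers in Enrollment and Participants:

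- Per ROST participant: 1 baseline + 8 sessions + 1 post-treatment + 1 follow-up = 11. Per control participant: 1 + 1 + 1 = 3.
- 160 baselines + 42 × 8 = 336 session attendances + 84 × 2 = 168 later interviews: 160 + 336 + 168 = 664.
- If all 103 expected at randomization are followed: 160 + 336 + 103 × 2 = 160 + 336 + 206 = 702.

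The 160 is the plan's figure, although 0.80 × 177 = 141.6. With 142 baselines and the rest unchanged, the first total is 142 + 336 + 168 = 646. The telephone screen is not counted. Follow-up interviews, read literally, follows all baseline completers, which gives more: 160 + 336 + 160 × 2 = 816. These are counts of questions asked, not of emergencies.

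**The case against.** A reader might infer that the risk protocol works only for someone seen at home. The text does not support that. High-risk item d offers constant telephone contact, moderate-risk item e is conducted by telephone, and clinical backup is summoned by phone or text. Home wording is not simply out of date either, since Assessment retention allows home interviews.

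Other safeguards are real:

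- In virtual sessions, measures are completed while research staff are still in the Zoom room, and moderate or high risk goes at once to licensed clinical backup (In-Session Measures).
- Backup staff are trained in risk assessment and safety planning (Clinical Backup).
- A safety-monitoring plan is promised for the wait before assignment and for follow-up, and worsening or risk of harm at a scheduled reassessment leads to a repeat face-to-face assessment (Removing Participants from the Protocol).
- Clinicians are obliged to "act in a manner that is most protective of their own safety", and a competent one would probably ask for the location.

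Imminent risk is excluded at entry, and high-risk item c is reached only after several refusals. The cited health-system standards are not in the supplied file and may contain a location check.

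All of this stands and keeps the expected number of events low. It does not fill the gap: none of these provisions establishes where a remote participant is, and the repeat face-to-face assessment is not an immediate emergency step.

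**Conclusion.** The point holds as a specific, inexpensive safety improvement. Dispatch is tied to the home, remote contact is a standing option in both arms, and no supplied step confirms current location. The two in-person statements are wrong as they stand and need correcting whatever view is taken of the rest.

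Three stronger readings should be avoided:

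- That responders would have no address. One is collected and updated; it may just not be where the person is.
- That risk at a remote baseline would surface before an address is held. That is possible, but the order of questions within baseline is not stated.
- That the 664 or 702 contacts measure the danger. They measure workload if all contact were remote.

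The conclusion assumes that the supplied text is what staff follow; a location check in the cited health-system standards would reduce the main gap to a missing cross-reference. Events are expected to be few and cannot be counted. No estimate, power or error rate changes.

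**What to change.** 1. At the start of each phone or Zoom interview and each virtual ROST session, privately confirm current location and a call-back number. At a remote baseline, do so before any risk question. Make the answers, and the address and contact persons already held, available to the Research Associate and clinical backup in an emergency. If the health-system standards already require this, cite them instead.
2. In high-risk item c, send responders to the participant's current location.
3. In moderate- and high-risk item c, keep the condition for calling against the person's will. Add that, for a remote contact, it asks whether a family member or other trusted person able to ensure ongoing safety is physically with the participant, not counting study staff. Merely substituting wording about someone being with the participant could change the condition: staff are always present at a church session, and any companion might seem to satisfy it remotely.
4. Leave moderate-risk item d and high-risk items d and e unchanged.
5. Correct the in-person statements on the first interview and on consent to match Baseline Interview and Consent.

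**Cost.** One short private question per remote contact, a few wording changes, and no extra staff or visits. The downside is one more identifying field, to be stored apart from responses as other identifiers are, and the need for a private route in virtual groups, such as a one-to-one message before the group opens. The Background lists lack of anonymity as a barrier to seeking help, so that privacy matters. Clinical thresholds remain with the investigators.
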